# 8. Research question and objectives

The goal of this study is to assess the awareness of InductOs-using spine surgeons concerning heterotopic ossification in relation to the InductOs Risk Management Plan. A supplementary goal of this study is to gauge the clinician's awareness about the development of heterotopic ossification and the risk minimisation measures; specifically identifying from which source was any knowledge obtained.

#### Primary questions:

- Do physicians administering InductOs understand the potential for heterotopic ossification occurrence after spinal interbody fusion?
- Do physicians administering InductOs know the appropriate measures to be taken to minimize the risk of heterotopic ossification occurrence?

## Secondary question:

• Was the knowledge on the risk of heterotopic ossification and minimization measures obtained from the SmPC, educational materials, professional training and literature, or a combination of these?

## 9. Research methods

#### 9.1 Study design

This study is a cross-sectional cohort analysis of InductOs-using spine surgeons to establish:

• their current level of knowledge regarding heterotopic ossification,

 the current level of knowledge, and degree of access to or utilisation of educational materials about the potential for post-surgical heterotopic ossification and practical risk minimisation measures.

A cross-sectional cohort study methodology was judged to be appropriate to meet the expectations of the European Medicines Agency (EMA) based on:

- The nature of the medicinal product: single use implantation in a relatively small target population
- The nature of heterotopic ossification which is not an uncommon adverse event of many orthopaedic procedures and it does not always manifest clinically
- The lack of appropriate data fields captured in the national spine registries across Europe,
- The period over which the educational materials have been available (since summer 2017)

The cohort study will be composed of an anonymous, online survey (see Annex 3) with the aim of answering the study questions outlined in section 8.

The screening for eligibility and online interviews will be conducted in the surgeon's native language. All materials will be prepared using the English master questionnaire as the baseline (see Annex 3). Translations will undergo appropriate quality checks prior to sign off by the research team.

The researchers will secure responses from 55 individuals from the four selected countries split proportionally based on usage, see section 9.5.

A pilot project of 2 surgeons will test the survey for clarity and accuracy of response and translated materials in an iterative manner. If no changes are made, then the pilot recruits will be included in the main cohort.

#### 9.2 Setting

As the national spine registries at the time of this study do not record InductOs use or the incidence of heterotopic ossification, and no database of physicians who prescribe InductOs exists, a random or probability sample is not feasible for this cohort study.

A non-probability sample (i.e. convenience sample) of orthopaedic surgeons and neurosurgeons who have administered InductOs in the last 2 years (recent users) will be chosen from a pool of the four countries comprising the largest InductOs-selling countries (France, Germany, United Kingdom and Ireland).

Hospitals who have purchased the medicinal product in the 24 months prior to the cut-off date for confirmation of the 'involved study accounts' with the study researchers, will be identified from Medtronic sales records. The appropriate hospital clinicians will then be approached by the study researchers to identify and screen for surgeons meeting the inclusion/ exclusion criteria. Eligible surgeons will be invited to participate in an online interview to quantitatively extract the required information via a personal link by email, and up to two reminders will be sent if needed. The first reminder is sent by email after 2 days, the second reminder is sent after 5 days and the surgeon will be given a call at that time as well.

Any surgery where InductOs is implanted is conducted under supervision of a surgeon, including the preparation of the medicinal product. The main risk minimization measures are under the control of the surgeon, e.g. placing an additional barrier between implanted matrix and the spinal canal. Therefore, the target population for the survey has been determined to be surgeons only.

Participating physicians have the option to receive compensation for their time. The amount will be determined based on the maximum allowed for each country and a fair market value assessment, appropriate reporting or disclosure of physician reimbursement will comply with appropriate regulations and codes of practice; dependant on physician location.

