## 9.5 Study size

The minimum sample size needed to obtain a proportion with confidence interval with the lower limit above the 80 % minimum awareness was calculated. For this calculation an alfa of 0.05 with a two-sided interval and a distance from proportion to limit of 0.1 was used with the expected proportion of 90 %. This leads to a minimum sample size of 35.

To ensure inclusion of data from the different participating countries, this study aims at collecting responses from physicians covering roughly 10 % of purchasing pharmacies that have received InductOs in the past 2 years in each target country. However, if a greater number of respondents complete the questionnaires for a given target group, these responses will be integrated into the analyses.

The following number of completed surveys are planned per country:

France: 15Germany: 15

- United Kingdom: 15

- Ireland: 10

This brings the total to 55 completed surveys which is above the calculated minimum sample size. Taking into account response rate of roughly 60 % and screening failures an estimated 120 surgeons will be screened for eligibility.

Recruitment rate will be monitored by the researchers; and if it becomes apparent that the there is a risk of the study not meeting the recruitment target then other countries with InductOs sales will be included in the study to widen the pool of potential participants. In the selection of additional countries for recruitment, priority will be given to countries where the existing translated materials are used.

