#### 9.10 Limitations of the research methods

Potential limitations to using this online survey include:

- Non-response bias: This is an inherent limitation in the survey study design. The non-response rate is reduced through the use of a telephone screening, short survey and the potential for compensation for time.
- Social desirability response bias: Surgeons may respond positively rather than truthfully. In order to reduce the probability of this type of bias, surveys are anonymous, questions are not leading, and are designed to elicit truthful responses.
- Sample is not random: A random sample of individuals meeting the selection criteria equalises the potential for bias to occur, making the sample potentially useful for generalising to the overall population. However, the small number of potential surgeons who would meet the selection criteria effectively removes the potential for randomisation.
- Self-selection bias: Even with the selection criteria it may be only the most motivated, experienced or engaged surgeons who participate leading to artificially high rates of awareness. This is reduced by decreasing the non-response bias, see above. Furthermore, the sample is chosen from all current users in the countries, regardless of quantity of InductOs provided in the past years.

These limitations are acknowledged and, given the nature of the data collected, should not greatly impact the conclusions drawn from the data collected from respondents. Efforts, where possible, will be made to address and reduce the impact of these limitations, see bullets above.

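### Random sampling is ruled out for want of a physician list, yet the plan's own list of purchasing hospitals could be contacted in random order, and no rule says which of them are approached

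*Protocol*

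**What the plan says.** Protocol 9.2 (Setting) gives the absence of registry data and of a physician list as the reason for not sampling at random: "no database of physicians who prescribe InductOs exists, a random or probability sample is not feasible for this cohort study". It then specifies "A non-probability sample (i.e. convenience sample) of orthopaedic surgeons and neurosurgeons who have administered InductOs in the last 2 years", taken from four countries.

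The recruitment path in the same section has three steps:

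- Hospitals that purchased in the 24 months before a cut-off date "will be identified from Medtronic sales records".
- The researchers contact clinicians at those hospitals in order to find surgeons and check them against the entry criteria.
- "Eligible surgeons will be invited to participate in an online interview". No sub-selection within a hospital is described.

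Nothing in 9.2 says which listed hospitals are contacted, or in what order.

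Section 9.10 (Limitations) gives a different reason: "the small number of potential surgeons who would meet the selection criteria effectively removes the potential for randomisation". It also concedes that the most engaged surgeons may be the ones who respond, which would push measured awareness up.

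Section 9.5 (Study size) sets the coverage target at "roughly 10 % of purchasing pharmacies that have received InductOs in the past 2 years in each target country", with 15 completes each in France, Germany and the United Kingdom and 10 in Ireland, 55 in all. It assumes a response rate of about 60 % and 120 surgeons screened. Section 9.7 calls the measures effective if 44 or more of 55 respondents are aware.

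**The concern.** A probability sample does not need a list of the final units. A list of the hospitals in which they work is enough for the first stage, and 9.2 already produces one. The lack of a physician list therefore does not support the conclusion drawn from it.

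The second reason, in 9.10, sits badly with 9.5. If the planned completes cover only about a tenth of purchasing pharmacies, there are many more accounts than will be used. Some choice among them is then unavoidable, and the plan leaves it open.

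The study ends in a yes/no statement about effectiveness based on a simple count. If the accounts approached happen to be those with closer contact with the sponsor or heavier use, measured awareness could be raised by a route separate from the surgeons' own decision to respond. Unlike self-selection, the research team can remove this part by design.

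**Working it through.** **Inputs.** From 9.5: 55 completes; coverage about 10 %; response about 60 %; 120 screened; expected proportion 0.90, distance to the limit 0.10, two-sided alpha 0.05. From 9.7: success at 44 or more of 55. Assumed, not in the documents: respondents per account, the awareness gap between accounts, and the intraclass correlation (ICC).

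**1. The plan's own figure.** n = 1.96² × 0.9 × 0.1 / 0.1² = 34.57, rounded up to 35. This reproduces the stated minimum. Contact order does not affect it.

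**2. Implied number of accounts.** Frame = completes / (respondents per account × coverage).

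- One per account: 55 / (1 × 0.10) = 550.
- Two per account: 55 / (2 × 0.10) = 275.
- With coverage of 8 to 12 % and one to two respondents per account, the range is about 230 to 690.

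**3. Share of accounts approached.**

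- If each of the 120 screened surgeons comes from a different account: 120/550 = 22 %, or 120/275 = 44 %.
- If two are screened per account, 60 accounts are approached: 60/275 = 22 %.

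In each case fewer than half are approached.

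**4. Effect on the success rule.** Assume approached accounts are 85 % aware and the rest 75 %. Under random order, expected awareness is the average over the whole frame: 0.75 + 0.10 × share approached. The probabilities are exact binomial and treat respondents as independent.

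| Situation | Awareness sampled | P(44 or more of 55) |
|---|---|---|
| Only the better-informed accounts approached | 0.850 | 0.89 |
| Random order, better-informed share 120/550 (or 60/275) | 0.772 | 0.38 |
| Random order, better-informed share 120/275 | 0.794 | 0.53 |

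The last probability is 0.533 unrounded, and 0.54 if awareness is first rounded to 0.794. It is the cautious end of the range: it combines the smaller frame with one screened surgeon per account.

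A gap of another size can be read from these reference values: P(44 or more of 55) is 0.25 at 75 % awareness, 0.58 at 80 % and 0.89 at 85 %.

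**5. Clustering (secondary).** Design effect = 1 + (m − 1) × ICC. With m = 2 and an assumed ICC of 0.1 to 0.3, it is 1.1 to 1.3. Effective n is 55/1.1 = 50 to 55/1.3 = 42, still above 35.

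**The case against.** **The limitation is disclosed.** Section 9.2 names the convenience sample, and 9.10 lists both non-random sampling and self-selection, with the direction of bias. That is so. But disclosure does not make the infeasibility argument correct, and it does not remove a choice that could be removed.

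**The frame size is inferred and the list is imperfect.** This stands. The quotas are round numbers and the coverage is approximate. Section 9.1 speaks of a relatively small target population, and 9.5 plans to add countries if recruitment falls short. The product also has a tibia-fracture indication (section 7), so some purchasing accounts may have no eligible spine surgeon. The purchase window ends at an account cut-off date, while eligibility is counted back from the survey date. Section 9.2 speaks of hospitals and 9.5 of pharmacies. A reader might infer that 9.5 proves there are several hundred eligible surgeons. It does not; it shows only that the reason in 9.10 fits poorly with the plan's own target.

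**No hand-picking is described.** Also true. A reader might infer that the sponsor or the researchers will choose favourable accounts. The text does not say so; 9.10 states that the sample comes from all current users regardless of quantity supplied. The defect is that no rule for selection or contact order is given.

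**Random order would still give a volunteer sample.** Correct. With about 60 % response and hospital clinicians naming the surgeons, the change does not produce an unbiased estimate or give the confidence interval a full sampling basis.

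**Conclusion.** The point holds as a correctable design weakness. The reason given in 9.2 does not support ruling out random selection, the reason in 9.10 fits poorly with 9.5, and the selection of accounts is unregulated although fewer than half are likely to be approached.

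The size depends on an assumed gap. With 10 points between approached and other accounts, the chance of declaring the measures effective is 0.89, against about 0.38 to 0.53 under random order. The documents contain nothing that fixes the gap, so this shows sensitivity and does not estimate bias.

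Two stronger readings should be avoided:

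- A reader might compare 0.89 with 0.25, the pass probability at 75 % awareness. That figure describes the unapproached accounts alone, whereas a random order draws on all accounts, including the better-informed ones.
- A reader might infer that several respondents from one hospital undermine the success criterion. The criterion in 9.7 is a count, not a confidence limit, and is unaltered by the design effect. Clustering makes the descriptive interval modestly too narrow and no more.

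**What to change.** In 9.2:

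- Put the sales-record accounts in computer-generated random order within each country, and contact them in that order until the country quota is met.
- Invite all eligible surgeons at each contacted hospital. Taking one surgeon per hospital without weights would under-represent surgeons at hospitals with several users. Section 9.5 already accepts completes above quota, so the last hospital opened need not be cut short.
- Keep a contact log, and report contacted, refusing and responding accounts by purchase volume.
- Use one term for the listed unit in 9.2 and 9.5, and state how many accounts are listed per country.

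In 9.2 and 9.10, replace the infeasibility statements with what is true: no surgeon list exists, hospitals are selected at random from purchasers, and non-response, self-selection and reliance on hospital clinicians to name surgeons remain as limitations.

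The cost is a random sort of a list that the study draws up anyway, plus a log. The target of 55, the minimum of 35 and the 120 to be screened need not change. Fieldwork may take slightly longer because recruiters cannot begin with the easiest accounts. The change has to be made before contact starts, since no later analysis can restore it.

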# 7. Rationale and background

The active ingredient of InductOs is dibotermin alfa or recombinant human Bone Morphogenetic Protein 2. Its osteoinductive properties result in the induction of new bone tissue at the site of implantation.

InductOs is approved for:

- single-level lumbar interbody spine fusion as a substitute for autogenous bone graft in adults with degenerative disc disease who have had at least 6 months of non-operative treatment for this condition.
- treatment of acute tibia fractures in adults, as an adjunct to standard care using open fracture reduction and intramedullary unreamed nail fixation.

Instructions for proper preparation and administration of dibotermin alfa/ACS are provided in the Summary of Product Characteristics (SmPC) and instructions for reconstitution are provided in the labelling of the pack. The aforementioned instructions consist of routine measures to minimise important identified (heterotopic ossification, osteolysis/resorption bone increased, fluid collection) and potential risks (medication errors and incorrect use, malignancies, antibody formation) by providing information on the measures to take during administration of dibotermin alfa/ACS or situations to avoid.

Additional risk minimisation measures (aRMM) to increase awareness about the identified risk of heterotopic ossification (especially in posterior surgical approaches for lumbar interbody fusion) and the potential risk of medication errors and misuse are available in the form of educational materials. These educational materials also aim at providing guidance on how to manage these risks. The aRMM present the information from the Summary of

Product Characteristics (SmPC) supported with visual aids, e.g. a demonstration of the correct preparation technique. The aRMM and related educational materials contain no information which is not contained in the SmPC.

InductOs educational materials consist of a preparation guide, two videos (one for each indication), and the SmPC. The educational materials can be accessed through a dedicated website, or upon request to the MAH.

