#### Exclusion criteria

Participants meeting any of the following criteria will not be included in the study:

- 1. Physicians that participated in the testing of this survey, if there are substantial changes made to the survey post-pilot i.e. changes which, in the view of the research team, make the participants contributions invalid or potentially compromising of the study objectives
- 2. Physicians that either themselves work for or have immediate family members who work for Medtronic, third parties involved in this study, or a regulatory agency (EMA, MHRA, HPRA, ANSM, BfARM)

During the initial phone call, screening questions will be asked to determine the eligibility of the physician for participation.

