## 9.8 Quality control

A pre-test of the questionnaire will be performed to ensure its comprehensibility and consistency (see section 9.4).

Suazio will follow its procedures for quality control during the conduct of the survey, which includes but is not limited to:

- Randomization of answer options
- Consistency checks for plausible data
- Checks for completeness of data and perform follow-up as needed

Medtronic BioPharma will follow Medtronic BioPharma procedures and study specific plans will be followed for quality control, which includes but is not limited to:

- Documenting all statistical analysis programs used, including version number
- Archiving the original database and any derived data sets, and all relevant study documents in an electronic document system

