# **Participant Information and Consent**

The participants will receive a thorough briefing on the nature and purpose of the study to enable and inform their consent decision, see the questionnaire in Annex 3. Their consent will be recorded.

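### The primary awareness score comes from an unsupervised online test with no stated safeguard against looking up the answers, and section 9.10 does not list look-up as a bias

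*Protocol*

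**What the plan says.** **Delivery.** Under Protocol section 9.2 surgeons are first telephoned: "During the initial phone call, screening questions will be asked to determine the eligibility of the physician for participation". Those eligible are then invited to the online questionnaire "via a personal link by email, and up to two reminders will be sent if needed". On timing, the section says: "The first reminder is sent by email after 2 days, the second reminder is sent after 5 days and the surgeon will be given a" telephone call. It states no closing time, and no rule on pausing, resuming or going back.

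**Where the answers are.** Section 7 says: "The educational materials can be accessed through a dedicated website, or upon request to the MAH". It adds: "The aRMM and related educational materials contain no information which is not contained in the SmPC". Every point that the materials teach can therefore also be found in the SmPC.

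**Briefing.** Section 10 says: "The participants will receive a thorough briefing on the nature and purpose of the study to enable and inform their consent decision". It refers the reader to the questionnaire in Annex 3 for this.

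**Questionnaire.** Annex 3 asks yes or no on a list of adverse reactions, one of which is heterotopic ossification. The introduction to the true/false block that follows tells the respondent that heterotopic ossification is a known adverse reaction to the product. No item or instruction in Annex 3 as shown concerns the use of reference material while answering.

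**Controls and limitations.** For the survey vendor, section 9.8 lists "Randomization of answer options", plausibility checks and completeness checks, and says that the list is not exhaustive. Section 9.10 opens with "Potential limitations to using this online survey include" and names non-response, social desirability, the non-random sample and self-selection.

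**Decision rule.** Under section 9.7 a surgeon with at least 9 of 12 scored items correct is aware. The measures are judged effective if 80% of respondents are aware, that is 44 of the targeted 55.

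**The concern.** The study sets out to establish what surgeons currently know. An unsupervised online test with freely available answers can instead record what a surgeon can find when prompted. A respondent who opens the SmPC or the preparation guide in another window and then scores 9 of 12 counts as aware.

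The error runs one way. A correct look-up can turn an unaware respondent into an aware one, and it does not do the reverse. The success rule is a bare point estimate, so it has no margin to absorb such a bias. Section 7 records that the effectiveness evaluation may rest on process indicators alone, carefully interpreted, so this proportion carries the conclusion. Section 9.10 already recognises that self-selection could raise awareness artificially. Look-up would add to that in the same direction.

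The order of items in Annex 3 creates a smaller exposure of the same kind. If a respondent can go back, the introduction to the true/false block gives away the answer to the heterotopic ossification item just before it. The colour marking of scored items cannot be read in the text at hand, so whether that item is one of the 12 is not known. If it is, the effect is at most one point of 12.

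**Working it through.** **The plan's own figures**

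- Sample size (section 9.5: two-sided alpha 0.05, expected proportion 0.90, distance to limit 0.10): n = 1.96² × 0.90 × 0.10 / 0.10² = 34.57, rounded up to 35. This reproduces.
- Individual cut-off: 0.75 × 12 = 9. Study rule: 0.80 × 55 = 44. Both reproduce.

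**Inputs that the documents do not give**

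- p, true unaided awareness. The only value in the protocol is the planning value of 90%. The range 60% to 90% is an assumption.
- q, the share of unaware surgeons who look up enough to pass. No value is given. The range 0 to 50% is an assumption.

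**Formulae**

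- Measured awareness: p' = p + (1 − p) × q.
- Chance of meeting the rule: P(X ≥ 44), with X binomial (55, p').
- Example: p = 0.70 and q = 0.20 give p' = 0.70 + 0.30 × 0.20 = 0.76, and P(X ≥ 44) = 0.303.

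**Chance of at least 44 of 55 aware**

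| True awareness p | q = 0 | q = 10% | q = 20% | q = 30% | q = 50% |
|---|---|---|---|---|---|
| 60% | 0.001 | 0.008 | 0.035 | 0.119 | 0.580 |
| 65% | 0.012 | 0.041 | 0.119 | 0.274 | 0.754 |
| 70% | 0.067 | 0.154 | 0.303 | 0.506 | 0.887 |
| 75% | 0.246 | 0.400 | 0.580 | 0.754 | 0.963 |
| 90% | 0.993 | 0.997 | 0.999 | 1.000 | 1.000 |

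**Look-up needed for measured awareness of 80%:** q = (0.80 − p) / (1 − p).

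- p = 0.75: 0.05 / 0.25 = 20%.
- p = 0.70: 0.10 / 0.30 = 33%. At exactly one third, p' = 0.80 and the chance of meeting the rule is 0.580.
- p = 0.65: 0.15 / 0.35 = 43%.
- p = 0.60: 0.20 / 0.40 = 50%.

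Look-up therefore hardly matters if awareness is as planned. It matters when awareness is moderately below 80%, which is where the study has to be able to show a shortfall.

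**The case against.** The strongest reply has four parts.

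**Timing.** A reader might infer from the briefing and the reminders that surgeons learn the purpose days ahead and can study the answers before the test. The documents do not show this. Section 10 points to the questionnaire for the briefing, so it may be the first screen after the link is opened. The only stated earlier contact is the screening call, whose script is not given. Reminders go out only if needed, so they show when a surgeon may still start. They do not show that the questions can be opened, left and resumed. This part stands. It does not remove the exposure, because a surgeon briefed on the first screen can still open another window.

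**Safeguards may exist.** The list in 9.8 is open-ended, and session settings often sit in a survey programming specification. It would be too strong to say that nothing prevents look-up. What can be said is that the protocol commits to no safeguard, that the questionnaire text, which is fixed in Annex 3, has none, and that 9.10 omits the bias.

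**Weak motive.** The survey is short and anonymous, and 9.10 says that the questions are designed to draw truthful answers. This lowers the incentive to look up. It does not address a conscientious respondent who checks a source because nobody asked them not to.

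**Assumed size.** The look-up rate is invented, and at the planning value of 90% nothing changes. Both points are correct. They limit the claim to a possible bias with a range.

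**Conclusion.** The point holds as a design weakness that should be closed before launch. The primary endpoint is an unsupervised knowledge test with freely accessible answers. Annex 3 does not ask for answers from memory, there is no check on sources consulted, no rule against going back is stated, and look-up is missing from the limitations.

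Measured awareness may be inflated; the documents do not show that it is. The size depends on two assumptions, true awareness and the share of unaware surgeons who look up and pass. At 70% true awareness, look-up by 10% to one third of the unaware raises the chance of meeting the 44-of-55 rule from 0.07 to between 0.15 and 0.58. At 75%, look-up by 20% raises it from 0.25 to 0.58. At 90% it is at least 0.993 with or without look-up. The model also assumes independent respondents and that look-up never lowers a score.

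**What to change.** - **Annex 3, 9.2 and 9.8:** put an on-screen instruction before the knowledge block to answer from memory without consulting materials. Disable back-navigation within that block, which must begin with the adverse-reaction list so that its items cannot be changed after the true/false introduction is seen. Record page times. Add a closing question on whether any source was consulted while answering.
- **9.7:** as a sensitivity analysis, repeat the primary proportion without respondents who report look-up. This corrects only part of the bias, because those removed are mostly unaware. With p = 0.70 and q = one third, and only unaware surgeons looking up, it gives 0.70 / 0.90 = 0.78 against a true 0.70. Counting the same respondents as not aware would give a lower bound at no further cost in data. Both depend on honest reporting.
- **9.10:** list look-up as a bias towards higher awareness.

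Two things should stay as they are. The full consent briefing should remain, because a deliberately vague statement of purpose would conflict with section 10. Slow or interrupted completion should not exclude anyone from the primary analysis, because surgeons are interrupted by clinical work and the target is only 55.

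The cost is one extra question, one extra analysis and slightly less convenient navigation.
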